3.2 Inclusion Criteria

- 3.2.1 Biopsy proven breast carcinoma which is persistent and metastatic or recurrent and metastatic.
- 3.2.2 Patients must have failed at least one line of chemotherapy for metastatic disease.
- 3.2.3 Patients who are HER2+ as defined by ASCO CAP guidelines must have failed all prior therapy known to confer clinical benefit
- 3.2.4 Patients must have at least 3 distinct metastatic sites with at least one measurable lesion which is at least 1 cm or larger in largest diameter.
- 3.2.5 At the time of enrollment, patients must be ≥ 4 weeks[‡] since all of the following treatments (and recovered from the toxicity of prior treatment to \leq Grade 1, exclusive of alopecia):
 - major surgery;
 - radiotherapy;
 - chemotherapy (note: must be ≥ 6 weeks since therapy if treated with a nitrosourea, mitomycin, or monoclonal antibodies such as bevacizumab);
 - immunotherapy;
 - Biotherapy/targeted therapies.
([‡] - Patients can begin two weeks from prior treatment if they are asymptomatic from previous therapy)
- 3.2.6 Patient ≥ 18 years of age.
- 3.2.7 Patient life expectancy > 6 months.
- 3.2.8 ECOG status of 0 or 1
- 3.2.9 Adequate organ function including:
 - a) Marrow: Hemoglobin ≥ 10.0 g/dL, absolute neutrophil count (ANC) $\geq 1,500/\text{mm}^3$, and platelets $\geq 100,000/\text{mm}^3$.
 - b) Hepatic: Serum total bilirubin $\leq 1.5 \times$ upper limit of normal (ULN)
(Patients with Gilbert's Disease may be included if their total bilirubin is ≤ 3.0 mg/dL), alanine aminotransferase (ALT), and aspartate aminotransferase (AST) $\leq 2.5 \times$ ULN. If the patient has known liver metastases, an ALT and/or AST $\leq 5 \times$ ULN are allowed.
 - c) Renal: Estimated or measured creatinine clearance ≥ 60 mL/min.
 - d) Other: Prothrombin time (PT) and partial thromboplastin time (PTT) $<$ ULN.
- 3.2.10 Patients must have negative tests (antibody and/or antigen) for hepatitis

viruses B and C unless the result is consistent with prior vaccination or prior infection with full recovery.

- 3.2.11 Male and female patients of child-producing potential must agree to use effective contraception while enrolled on study and receiving the experimental drug, and for at least 3 months after the last treatment.
- 3.2.12 Ability to understand and the willingness to sign a written informed consent document. Patients may not be consented by a durable power of attorney.

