5.3 On-Study Evaluations

(See study calendar, section 5.10)

1. Physical exam: including complete skin evaluation and evaluation of oral mucosa prior to start of **each** RT cycle and **prior** to each LY2157299 administration.
2. Hematology: CBC with differential and platelet count and peripheral blood smear. PT/INR,PTT should be evaluated following multiple doses of LY2157299; Serum chemistries: Electrolytes (sodium, potassium, chloride, and bicarbonate), BUN, creatinine, glucose, and liver function tests (AST, ALT, ALP, total bilirubin, LDH, and Troponin I C). These will be carried out prior to start of each RT cycle and prior to each cycle of 2 weeks of BID LY2157299 administration.
3. ECHO/Doppler : Week 8 within 5 days prior to starting week 9 LY2157299 administration and Week 15
4. Study Special Tests: TGF β levels (at wk 1 day -1 and week 15 visit), immune evaluation at weeks 1 day -1, 2, 5 and 15 LY2157299 PK (pre- & after completion of drug cycle day 14 & at day 42).
5. Tumor measurement by PET/CT/ CT(chest/abdomen/pelvis) at weeks 5 and 15.
6. Adverse events evaluated and recorded using the NCI CTCAE version 4.0 throughout the treatment period (weeks 0-15).

To date, LY2157299 at the planned dose for this study is well tolerated in patients. If a toxicity is observed, a dose reduction may be considered based on the aggregate safety information of LY2157299, if other plausible reasons for a toxicity have been excluded.

Specifically, no bone marrow toxicities were detected in nonclinical toxicology studies; 1 toxicity was reported in a patient with glioblastoma in whom a Grade 4 thrombocytopenia was observed and this toxicity was potentially associated with administration of LY2157299 monotherapy. If a similar case occurs, the drug should be discontinued until platelet counts either return to Grade 1 or baseline.

If a patient experiences any of the following events that are considered possibly related to LY2157299 and not to study disease, LY2157299 will be omitted until the event resolves:

- Grade 4 Thrombocytopenia
- Grade 3 thrombocytopenia associated with bleeding
- Grade 4 Anemia
- absolute neutrophil count (ANC) $<0.5 \times 10^9/L$ for longer than 7 days, or ANC $<1.0 \times 10^9/L$ with a single temperature of $>101^{\circ}\text{F}/38.3^{\circ}\text{C}$ or a sustained temperature of $>100.4^{\circ}\text{F}/38^{\circ}\text{C}$ for more than 1 hour, or platelet count $<25,000 \times 10^9/L$

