- Common Terminology Criteria for Adverse Events Grade 3 or 4 non-hematologic toxicity

Non-hematologic and hematologic toxicity must resolve to CTCAE Grade 0, 1, or baseline (with the exception of alopecia, fatigue, skin rash, nausea, vomiting, constipation, or diarrhea that can be controlled with treatment) before start of next cycle. If recovery is >29 days (Day 1 of the next cycle), patient must be withdrawn from study treatment.

If moderate or severe heart valve toxicities are observed, or the patient develops aneurysms of the great vessels of the heart, the patient must immediately be discontinued from the treatment and the toxicity reported to sponsor within 24 hours (see references on the ECHO assessment based on the Guidelines of the American and European Societies of Cardiac Echocardiography). If the patient develops new cardiovascular lesions in the chest, an MRI or CT with contrast of the abdomen should be performed to evaluate for development of abdominal vascular lesions. Exceptions to this rule must be approved by the IRBs and sponsor.

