11.1 Anti-tumor Effect

11.1.1 Definitions

Patients will be evaluated by PET/CT or CT(chest/abdomen/pelvis) at baseline, week 5 and week 15. However, systemic anti-tumor response will be by PET/CT or CT(chest/abdomen/pelvis) as defined by irRC at 15 weeks (primary endpoint).

Patients who have received at least one 14 days cycle of the study drug will be followed for toxicity (lack of grade 4 toxicity— primary safety end point). Patients will receive a total of 14 doses of LY2157299 (one dose daily for 14 consecutive days), per cycle. Patients who have received any treatment will also be evaluated for abscopal response to the metastatic sites using the immunologic response criteria based on the 5 and 15 week PET/CT or CT(chest/abdomen/pelvis) scans as outlined above in Table 2.

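### The numeric platelet limit for omitting LY2157299 in Section 5.3 is misscaled: 1,000 times too high if 25,000/mm³ was meant

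*Combined protocol and SAP*

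**What the plan says.** Section 5.3 (On-Study Evaluations) introduces its drug-hold list with "If a patient experiences any of the following events that are considered possibly related to LY2157299 and not to study disease" and directs that the drug be omitted until the event resolves. Two bullets define platelet events by grade: Grade 4 thrombocytopenia, and Grade 3 with bleeding. Neither carries a number. A later bullet gives numeric blood-count limits. It opens with "absolute neutrophil count (ANC) $<0.5 \times 10^9/L$ for longer than 7 days", adds a second neutrophil limit of 1.0 × 10⁹/L combined with fever, and ends with "platelet count $<25,000 \times 10^9/L".

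The only other numeric platelet limit in the protocol is the entry criterion in Section 3.2.9: "platelets $\geq 100,000/\text{mm}^3". The matching neutrophil entry criterion is "absolute neutrophil count (ANC) $\geq 1,500/\text{mm}^3".

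For restarting, Section 5.3 states: "Non-hematologic and hematologic toxicity must resolve to CTCAE Grade 0, 1, or baseline", with listed exceptions, before the next cycle begins. Section 7 (Dosing Delays/Dose Modifications) gives only the flat daily dose and its twice-daily split, with no thresholds.

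**The concern.** A trigger for withholding drug because platelets have fallen must lie below the level at which patients may enter. The printed limit lies far above it, so every eligible patient who enters at or near the minimum is already under the limit before the first dose.

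The attribution condition means this does not hold drug in everyone on day 1. Read literally, though, any platelet fall attributed to LY2157299, however small, would meet the trigger. Staff must then either follow a number that makes no clinical sense or substitute their own, and the two sites (WCM and UCLA) need not choose the same one.

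Platelets matter for this drug. Section 2.2.3 reports 2 unexplained cases of drug-related severe thrombocytopenia, Section 5.3 describes a Grade 4 case, and Section 8.5 lists thrombocytopenia as a possible side effect. The study-level rule in Section 12.2 counts only non-hematological toxicities, so the list in 5.3 is where blood toxicity is acted on.

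**Working it through.** The limit is a set value with no formula behind it, so the check is a unit conversion and a comparison with the entry criteria.

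**Conversion.** 1 L = 10⁶ mm³, so a count per litre divided by 10⁶ gives the count per mm³, and 1,000/mm³ = 1 × 10⁹/L.

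**Platelet trigger as printed (5.3).** 25,000 × 10⁹/L = 2.5 × 10¹³/L. Dividing by 10⁶ gives 25,000,000/mm³.

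**Platelet entry minimum (3.2.9).** 100,000/mm³ × 10⁶ = 10¹¹/L = 100 × 10⁹/L.

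**Printed trigger against entry minimum.** 25,000 / 100 = 250.

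**Trigger if 25,000/mm³ was meant (assumption).** 25,000 × 10⁶ = 2.5 × 10¹⁰/L = 25 × 10⁹/L. Printed against assumed: 25,000 / 25 = 1,000. Assumed against entry minimum: 25 / 100 = 0.25.

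**Control: neutrophils in the same bullet and unit.** The entry minimum is 1,500/mm³ = 1.5 × 10⁹/L.

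| Limit | In 10⁹/L | Per mm³ | Ratio to entry minimum |
|---|---|---|---|
| Neutrophils, first limit | 0.5 | 500 | 0.5 / 1.5 = 0.33 |
| Neutrophils, second limit | 1.0 | 1,000 | 1.0 / 1.5 = 0.67 |
| Platelets, as printed | 25,000 | 25,000,000 | 250 |
| Platelets, if 25,000/mm³ meant | 25 | 25,000 | 0.25 |

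The neutrophil limits sit below their entry minimum, as hold limits should. The platelet limit does so only after the correction. The pattern fits a per-mm³ number printed with a per-litre multiplier.

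**The case against.** The best case on the other side is that this is a slip any trained reader would recognise and that it harms no one. The entry criterion and the neighbouring neutrophil limits point to the presumed meaning. The two graded thrombocytopenia triggers work without the number. Every trigger needs a judgment of possible relation to the drug. The literal error leads to holding drug too readily, not to continuing it in a patient with low platelets. The restart rule also allows treatment at Grade 0, Grade 1 or baseline, so a trivial fall would already be at the level for resuming. The primary safety endpoint is "lack of grade 4 toxicity", and neither it nor the sample size or analysis uses the figure.

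Most of this stands, and it limits the consequence. The restart point does not remove the error, because that rule governs when dosing may resume and not whether the trigger is met. A reader applying both would find the count still under the printed limit while the restart rule permits dosing. That the right value can be guessed does not excuse the wrong one in a dosing rule.

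It is also fair that the documents do not show whether the numeral, the exponent or the unit is at fault. An exponent of 6 would give exactly 25,000/mm³ and no error. The exponent is worth a glance at the printed page, but nothing suggests it was misread, and the exponents on the neutrophil limits in the same bullet are right.

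**Conclusion.** The concern holds. The printed platelet trigger is 25,000,000/mm³, 250 times the entry minimum, and cannot serve as a hold limit. That conclusion needs only Sections 5.3 and 3.2.9. The factor of 1,000 rests on the further assumption that 25,000/mm³ was intended, a value the documents never state. The practical effect is limited for the reasons already given, but an operative threshold for withholding study drug is wrong as written, so it should be fixed.

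**What to change.** In Section 5.3, replace the platelet limit with <25 × 10⁹/L, adding <25,000/mm³ in brackets so that it reads directly against Section 3.2.9. The sponsor and investigators should first confirm that this is the intended value. The graded thrombocytopenia bullets and the neutrophil limits need no change. The cost is a one-line protocol correction, with no effect on design, sample size, analysis or patient burden.

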5.4 General Concomitant Medication and Supportive Care Guidelines

No concomitant cancer therapies, immunosuppressive agents or anti-coagulation therapies are permitted during the study unless specified below. Inhaled or topical corticosteroids are allowed.

Use of alternative medications (herbals, botanicals, etc.) is strongly discouraged during the entire study period. In addition, starting new medications other than anti-cancer agents may be associated with side effects; therefore, medications should not be started for the first time during or around the time of LY2157299 administration.

5.5 Duration of Therapy

Patients completing the week 15 visit will have completed the study treatment.

5.6 Duration of Follow Up

Patients will be followed with follow-up visits monthly for the first three months after completing therapy then annually for 5 years with physical exam, performance status evaluation, labs and Echocardiography and Doppler (see study calendar, section 5.10).

5.7 Criteria for Removal from Study

Patients may withdraw consent and discontinue participation in the study at any time, without prejudice to further treatment. A patient's participation in the study may also be discontinued at any time at the discretion of the Investigator.

The following are reasons why the Investigator may remove a patient from study treatment and further follow-up:

- The patient withdraws consent;
- The patient is found to be not eligible after enrollment;
- The patient is non-compliant with study requirements;
- The Study is terminated

The following are reasons why the Investigator or Sponsor may remove a patient from study treatment but continue follow-up:

- General or specific changes in the patient's condition render the patient unacceptable for further treatment per the investigator's judgment;

IND # 126952

- The patient becomes pregnant during the study (note: patients who become pregnant during the study must be followed throughout their pregnancy; it will also be important to follow any infants exposed to LY2157299 during fetal development);
- The patient suffers an intolerable AE;
- The patient develops progressive disease (progression at week 5 PET/CT or CT(chest/abdomen/pelvis) does not warrant study discontinuation if clinically stable);
- The patient requires a prohibited medication;
- There is new information to suggest a significant change in risk/benefit for LY2157299;

5.8 Alternatives

Standard of care treatment will be offered to all eligible patients.

5.9 Compensation

Patients will receive no compensation for participating in the trial.

5.10 Study Calendar

	Pre-Study	Wk 1 (Day -1) 0	Wk 1 (Day +1) (+/- 3 days)	Wk 2 (+/- 3 days)	Wk 3 (+/- 3 days)	Wk 4 (+/- 8 days)	Wk 5 (+/- 3 days)	Wk 6 (+/- 3 days)	Wk 7 (+/- 3 days)	Wk 8 (+/- 3 days)	Wk 9 (+/- 8 days)	Wk 10 (+/- 3 days)	Wk 11 (+/- 3 days)	Wk 12 (+/- 3 days)	Wk 13 (+/- 3 days)	Wk 14 (+/- 3 days)	Wk 15 (+/- 8 days)	Follow-up
Investigational Agent LY2157299^a			X	X ^{a,d}			X	X ^{a,d}			X ^{a,d}	X ^{a,d}			X ^{a,d}	X ^{a,d}		
RT				X ^d				X ^d										
Informed consent	X																	
Demographics	X																	
Medical history	X																	
EKG ^b	X ^b																	
Concurrent meds	X			X-----										X				
B-HCG ^c	X ^c																	
Performance status	X	X		X		X		X						X		X ^d	X	
Physical exam ^d (Vital signs)	X ^d	X ^d		X ^d		X ^d		X ^d		X ^d		X ^d		X ^d		X ^d	X	
CBC w/diff, plts, Serum chemistry ^e CEA/CA 27.29 ^f	X ^{e,f}	X ^e		X ^e	X ^e		X ^f	X ^e		X ^e	X ^e			X ^e		X ^{e,f}		
PT/INR/PTT	X	X		X	X			X		X	X			X			X	
Hepatitis B and C HbSAG, HCV Ab (antibody and/or antigen)	X																	

IND # 126952

Stool fecal occult blood test (2 consecutive)	X															
Adverse event evaluation			X-----											X		
PET/CT/CT(CAP)	X						X								X	
MRI or Brain CT with contrast	X															
Tumor tissue for TBRS signature	X ^g															
Blood draw for VEGF		X		X			X								X	
Blood draw for immunological studies		X		X			X								X	
Blood draw (pre and post) for LY2157299 pK		X								X						
Blood draw for LY2157299 cardiotoxicity (Troponin I)	X	X				X			X			X			X	
Echo/Doppler	X								X					X	X	
a: LY2157299 Administration of investigational drug is given 14 days on and 14 off. B: Before 1 st RT & repeated during the study if indicated. C: Serum pregnancy test (women of childbearing potential). D: PE must include full vital signs, skin and oral mucosa exam and prior to each LY2157299 administration and each RT cycle. PE continue monthly for the first 3 months following therapy then yearly for 5 years. E: Albumin, alkaline phosphatase, total bilirubin, bicarbonate, BUN, calcium, chloride, creatinine, glucose, LDH, phosphorus, potassium, total protein, SGOT[AST], SGPT[ALT], sodium f. CEA/CA 27.29 if elevated at baseline will be repeated at weeks 5 and 15. g. Archival tissue.																

6 PHARMACEUTICAL INFORMATION

6.1 Investigational Agent

LY2157299 is a receptor kinase inhibitor of TGF receptor type I (ALK5).

Packaging and Labeling

LY2157299 will be supplied in open-label blister packs or other appropriate packaging of film-coated, paracapsule tablets that are light yellow/yellow in appearance.

Drug Shipment and Storage

Eli Lilly & Co. will provide the clinical material for this study.

6.2 Availability

Full records must be maintained to account for the study drug supplied to the Investigators, the disposition of the study drug, and the return or destruction of unused supplies.

6.3 Agent Accountability

All investigational drugs are stored with the Investigational Pharmacy. A separate binder is issued to each study as well as a bin for storage. The bins and binder are labeled with the protocol number and drug name. At WCM, the Investigational Pharmacy is located in a separate room within the Inpatient Pharmacy. There is limited access, and only the Pharmacists and support personnel working in the Research Pharmacy have access. The hours of operation are Monday- Friday from 8-5pm. At the end of the day the room is locked. The research Pharmacist and staff can open the room using magnetic ID badges. Only the Research staff and management can enter the research area. Initial shipment of the investigational agent (LY2157299) will be delivered to WCM Investigational Pharmacy, which will disburse the agent within the WCM research group and to all collaborating institutions.

At UCLA, the Investigational Pharmacy is located in the Ronald Regan Medical Center. There is limited access, and only the Pharmacists and support personnel working in the Research Pharmacy have access. The hours of operation are Monday- Friday from 8-5pm. This area is locked at all times.

7 DOSING DELAYS/DOSE MODIFICATIONS

LY2157299 will be administered as a flat dose of 300 mg/day, divided in a BID administration of 150 mg each, as an oral tablet.

8 ADVERSE EVENTS: LIST AND REPORTING REQUIREMENTS

8.1 Adverse Events and Potential Risks List

LY2157299 has no reported history of Adverse Events or Serious Adverse Events.

CTCAE term (AE description) and grade: The descriptions and grading scales found in the revised NCI Common Terminology Criteria for Adverse Events (CTCAE) version 4.0 will be utilized for AE reporting. A copy of the CTCAE version 4.0 can be downloaded from the CTEP web site (<http://ctep.cancer.gov>).

Attribution of the AE:

Definite – The AE *is clearly related* to the study treatment.

Probable – The AE *is likely related* to the study treatment.

Possible – The AE *may be related* to the study treatment.

Unlikely – The AE *is doubtfully related* to the study treatment.

Unrelated – The AE *is clearly NOT related* to the study treatment

8.1.1 Recording of Adverse Events

All adverse events will be recorded on a patient specific AE log. The AE log will be maintained by the research staff and kept in the patient's research chart.

8.1.2 Reporting of AE to WCM IRB

All AEs occurring on this study will be reported to the IRB according to the IRB policy, which can be accessed via the following link:

http://researchintegrity.weill.cornell.edu/forms_and_policies/forms/Immediate_Reporting_Policy.pdf.

8.2 Expedited Adverse Event Reporting

The principal investigator is responsible for monitoring the safety of patients who enroll in the study. All AEs occurring after any administration of the study drug will be followed until resolution. The descriptions and grading scales found in the revised NCI CTCAE version 4.0 will be used for adverse event reporting. A copy of the CTCAE version 4.0 can be downloaded from the CTEP web site (<http://ctep.cancer.gov/reporting/ctc.html>).

A serious adverse event (SAE) is any adverse drug experience that occurs at any dose that results in any of the following outcomes:

- Death.
- Life-threatening adverse drug experience.
- Requires inpatient hospitalization or prolongation of existing hospitalization.

- For the purpose of this study, hospitalizations for protocol-scheduled procedures, blood product transfusions, or for social reasons (i.e., awaiting transport home) will not be considered SAEs.
- Persistent or significant disability/incapacity.
- A congenital anomaly/birth defect.
- Important medical events: Defined as AEs that, based upon appropriate medical judgment, may jeopardize the patient and may require medical or surgical intervention to prevent 1 of the outcomes listed above, even though these events may not be immediately life-threatening or result in death or hospitalization.

All SAEs occurring on this study will be reported to the IRB according to the IRB policy, which can be accessed via the following link:

http://researchintegrity.weill.cornell.edu/forms_and_policies/forms/Immediate_Reporting_Policy.pdf

8.3 Reporting Serious Adverse Events

All new SAEs and Medical Events of Interest occurring during the study or within 45 days of the last administration of LY2157299 will be reported as long as the patient has not withdrawn consent. The principal investigators are responsible for reporting SAEs to the IRB and the FDA (21 CFR §312.32] or other applicable regulatory authority. The principal investigator is responsible for submitting follow-up reports for all SAEs regarding the patient's subsequent course until the SAE has resolved or until the patient's condition stabilizes (in the case of persistent impairment), or the patient dies.

Institution and Investigator understand and agree that Investigator and Institution are obligated under applicable law and regulations to report any serious and related adverse event, if any that occurs during treatment with the Product to the Institution's IRB/Ethics Committee and to the governing regulatory authority in accordance with applicable filing timelines promptly after any such event occurs. Investigator, within 24 hours (US) or one business day (EU) of first knowledge of such serious and related adverse event, will notify Lilly's assigned medical Monitor.

Prior to or at the time of filing any such report with the governing regulatory authority, the Investigator will also transmit an information copy of the report as sent to the authorities to Lilly.

IND # 126952

Protocol # 1505016222
Version Date 04/21/2017

The Investigator shall make available to Eli Lilly promptly such records as may be necessary and pertinent to investigate any such expedited adverse event, if specifically requested by Lilly.

Furthermore, the Investigator will inform Eli Lilly of the following:

- any events that result in protocol amendments for safety reasons, as well as any safety related regulatory action such as a clinical hold of the Research
- any pregnancies occurring in patients who are exposed to the Product in connection with the Research.
- In addition, the Investigator shall notify Lilly within 24 hours (US) or one business day (EU) of first knowledge of any Product complaints (communication of dissatisfaction that alleges deficiencies related to the identity, quality, durability, effectiveness, safety, labeling, purity, stability, and appearance).

The Investigator will also inform Eli Lilly within 1 business day of becoming aware of any actions from any authority that may affect the performance of the Research

Medical Events of Interest

For reporting purposes, the Investigator will make note of any medical events of interest that occur during the treatment period.

